11.9.4. Statistical analysis

The statistical analysis will be conducted separately for the following:

- Treatment A versus Treatment C
- Treatment B versus Treatment C

Only the data for the comparison under investigation will be included in the statistical analysis i.e., when comparing Treatment A and Treatment C, the data for Treatment B will be removed from the dataset.

Subjects must have the primary PK parameter (C_{max} , $AUC_{(0-t)}$ or AUC) available for both treatments for the given analyte under consideration (for either ticagrelor or AR-C124910XX) in order to be included in a specific analysis; a subject may therefore be included in one or two comparisons for a given analyte and parameter.

The ratios of C_{max} , $AUC_{(0-t)}$ and AUC of both ticagrelor and AR-C124910XX will be obtained using a two-sided 90% CI approach based on an analysis of variance (ANOVA) model including fixed effects for treatment, sequence, period and subject within sequence. For exploratory purposes, the ANOVA as outlined here will be repeated with a random effect of subject within sequence. Additionally, the 90% CI for the difference in t_{max} will be calculated.

Bioequivalence may be concluded if the 90% CI of the ratios for both C_{max} and $AUC_{(0-t)}$ for both analytes are contained completely within the limits of 0.80-1.25.

Primary PK parameters will be log-transformed prior to analysis. The estimated treatment differences and the 90% CIs on the log scale will be back-transformed to obtain the geometric mean ratios for each pair of treatments. The least squares means (and 95% CIs for each), geometric mean ratios and 90% CIs will be tabulated for each treatment and analyte (ticagrelor and AR-C124910XX). The same ANOVA model will be applied to $t_{/2\lambda z}$, kel and MRT using log-transformed values [2].

In the analyses no adjustments will be made for multiple comparisons.

11.10. Analysis of safety data

The analysis of the safety variables will be based on the safety analysis set.

11.10.1. Adverse events

All AEs will be coded using MedDRA, and will be listed for each subject. A treatment-emergent adverse event (TEAE) is defined as an AE with onset (start date/time)

after the first dose of IMP in Treatment period 1. Adverse events will be assigned to a treatment based on the start date/time of the AE:

- Screening: AEs with start date/time prior to dosing in Treatment period 1.
- Treatment period 1: AEs with start date/time at the time of or after dosing in Treatment period 1 until the time of dosing in Treatment period 2.
- Treatment period 2: AEs with start date/time at the time of or after dosing in Treatment period 2 until the time of dosing in Treatment period 3.
- Treatment period 3: AEs with start date/time at the time of or after dosing in Treatment period 3 until the follow-up visit.

In the statistical output, AEs with missing start dates/times will be handled as follows:

- If the start date is completely missing the date will be imputed as the first day of dosing (Treatment period 1) unless a known end date shows otherwise in which case the screening date will be used
- If the start day is missing the day will be imputed as the first day on which a dose was given in that month unless a known end date shows otherwise, in which case the date will be imputed as 01. If the month is not a dosing month the date will be imputed as 01.
- If the start day and month is missing the date will be imputed as the first day of dosing in the known year unless a known end date shows otherwise in which case the screening date will be used. If the year is not a year of dosing then the date will be imputed as 01Jan
- Missing times will be imputed as 00:00 h or with the time of dosing for events starting on a dosing day

Adverse events will be summarized by treatment and overall, including tabulations by causality and severity (mild, moderate and severe). All tabulations will be presented by SOC and PT. Furthermore, listings of SAEs and AEs that led to discontinuation will be made and the number of subjects who had any AEs, SAEs, AEs that led to discontinuation, and AEs with outcome of death will be summarized. The AEs that occur before (first) dosing will be excluded from the summary tables.

The following information will be included in the listings: verbatim term, MedDRA SOC, PT and lowest level term, start date/time, end date/time, time from last dose, causality, action taken, whether the AE was classified as serious and the outcome.

All tabulations will include the number and percentage of subjects.

11.10.2. Vital signs and 12-lead electrocardiograms

The results of the vital signs measurements will be listed by subject and time-point including the date/time of the assessment, flags for measurements that are outside the reference range (L or H, if applicable), changes from baseline and repeat/unscheduled measurements. The baseline for these measurements will be the pre-dose measurements on Day 1 in each treatment period. Descriptive statistics will be presented by treatment and time-point for both observed values and changes from baseline. Screening and follow-up will be summarized separately, over all subjects and by time-point (screening or follow-up).

12-Lead ECG results will be listed for each subject.

11.10.3. Laboratory assessments

Hematology, clinical chemistry and coagulation values will be listed (including changes from baseline and repeat/unscheduled measurements, where applicable) and summarized overall by time-point (screening and follow-up, as applicable), where applicable, for all subjects in the safety analysis set. The baseline for the hematology and clinical chemistry tests will be the Screening values. Shift tables will also be presented.

Any laboratory parameters that are given as '<xx' or '>xx' in the database will be imputed with the absolute value of the number without the sign (e.g., <2.2 will be imputed as 2.2) for the descriptive statistics.

The listings will include the following information: test name, date of measurement, reference range, result and flags for any measurements that are outside the reference range (e.g., AZ, program, or laboratory ranges). Clinical laboratory data will be reported in the units provided by the clinical laboratory for the SRC meeting (if applicable), and in System International units in the CSR.

Additional listings will be presented for the following:

- Urinalysis (macroscopic and microscopic, if applicable)
- Pregnancy testing (including FSH)

11.10.4. Physical examination

The results of the physical examination will be listed by body system for each subject.

12.1. Definitions

12.

12.1.1. Definition of adverse events

ADVERSE EVENTS

An AE is the development of an undesirable medical condition or the deterioration of a pre-existing medical condition following or during exposure to a pharmaceutical product, whether or not considered causally related to the product.

An undesirable medical condition can be symptoms (e.g., nausea, chest pain), signs (e.g., tachycardia, enlarged liver) or the abnormal results of an investigation (e.g., laboratory findings, ECG).

In clinical studies an AE can include an undesirable medical condition occurring at any time after the subject/patient has signed informed consent, including run-in or washout periods, even if no specific treatment has been administered.

The term AE is used generally to include any AE whether serious or non-serious.

12.1.2. Definitions of serious adverse event

An SAE is an AE occurring during any study phase (i.e., run-in, treatment, washout, follow-up), that fulfills one or more of the following criteria:

- · Results in death
- Is immediately life-threatening
- Requires in-patient hospitalization or prolongation of existing hospitalization
- Results in persistent or significant disability or incapacity or substantial disruption of the ability to conduct normal life functions
- Is a congenital abnormality or birth defect
- Is an important medical event that may jeopardize the subject or may require medical intervention to prevent one of the outcomes listed above

For further guidance on the definition of an SAE, see Appendix 15.1 of this clinical study protocol.

12.1.3. Other significant adverse events

During the evaluation of the AE data, an AstraZeneca medically qualified expert will review the list of AEs that were not reported as SAEs or AEs leading to withdrawal. Based on the expert's judgment, significant AEs of particular clinical importance may, after consultation with the Global Safety Physician, be considered as other significant adverse events (OAEs) and reported as such in the CSR. A similar review of other data from vital signs, laboratory assessments and other safety assessments will be performed for identification of OAEs.

Examples of these are marked hematological and other laboratory abnormalities, and certain events that lead to intervention (other than those already classified as serious), dose reduction or significant additional treatment.

12.2. Recording of adverse events

12.2.1. Time period for collection of adverse events

SAEs will be collected from the signing of informed consent and AEs from randomization until the final follow-up visit.

12.2.2. Follow-up of unresolved adverse events

Any AEs that are unresolved at the subject's last visit in the study are followed up by the investigator for as long as medically indicated, but without further recording in ClinBase.

AstraZeneca retains the right to request additional information for any subject with ongoing AE(s)/SAE(s) at the end of the study, if judged necessary.

12.2.3. Variables

The following variables will be collected for each AE:

- AE diagnosis/description
- The date and time when the AE started and stopped
- Intensity
- Whether the AE is serious or not
- Investigator causality rating against the IMP (yes or no)
- AE caused subject's withdrawal from study (yes or no)
- Outcome

Additional variables (e.g., action taken with study drug) will be collected for all SAEs including treatment given for the event.

The following intensity ratings will be used:

1. mild (awareness of sign or symptom, but easily tolerated)

- 2. moderate (discomfort sufficient to cause interference with normal activities)
- 3. severe (incapacitating, with inability to perform normal activities)

It is important to distinguish between serious and severe AEs. Severity is a measure of intensity whereas seriousness is defined by the criteria in Section 12.1.2.

An AE of severe intensity need not necessarily be considered serious. For example, nausea that persists for several hours may be considered severe nausea, but not an SAE. On the other hand, a stroke that results in only a limited degree of disability may be considered a mild stroke but would be an SAE.

12.2.4. Causality collection

The investigator will assess causal relationship between IMP and each AE, and answer "yes" or "no" to the question "Do you consider that there is a reasonable possibility that the event may have been caused by the investigational product?"

For SAEs causal relationship will also be assessed for study procedures. Note that for SAEs that could be associated with any study procedure the causal relationship is implied as "yes".

A guide to the interpretation of the causality question is found in Appendix 15.1 of this clinical study protocol.

12.2.5. Adverse events based on signs and symptoms

All AEs spontaneously reported by the subject or reported in response to the open question from the study personnel: "Have you had any health problems since you were last asked?", or revealed by observation will be collected and recorded in ClinBase.

When collecting AEs the recording of diagnoses is preferred (when possible) to recording a list of symptoms and signs. However, if a diagnosis is known and there are other symptoms or signs that are not generally part of the diagnosis, the diagnosis and each symptom or sign will be recorded separately.

12.2.6. Adverse events based on examinations and tests

The results from protocol mandated safety assessments will be summarized in the CSR.

Deterioration as compared to baseline in protocol mandated safety assessments should therefore only be reported as AEs if they fulfill any of the SAE criteria.

If deterioration in a vital sign or laboratory value is associated with clinical symptoms and signs, the symptom or sign will be reported as an AE and the associated vital sign or laboratory result will be considered as additional information.

Wherever possible the reporting investigator should use the clinical, rather than the laboratory term (e.g., anemia versus low hemoglobin value).

In the absence of clinical symptoms or signs, clinically relevant deteriorations in non-mandated parameters should be reported as AE(s).

Any new or aggravated clinically relevant abnormal medical finding at a physical examination as compared with the baseline assessment will be reported as an AE.

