- Healthy subject decision. The healthy subject is at any time free to discontinue treatment, without prejudice to further treatment.
- Adverse event
- Severe noncompliance to study protocol
- Any significant and clinically relevant changes in the safety parameters (e.g., ECG, blood pressure, pulse, laboratory assessments and AEs) making the continuation of IMP administration unjustified.

- Study-specific withdrawal criteria: If a subject reports symptoms, which are considered unacceptable by the subject or the investigator, he/she will be withdrawn from the study. In particular:
 - Any moderate or severe bleeding event
 - Any other severe or serious adverse event (SAE) that is judged as possibly related to the IMPs by the investigator
 - Any case of Potential Hy's Law (PHL) according to Appendix 15.3

The appropriate AE form in the case report form (CRF) is to be completed.

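### Section 12.2.6 has no exception for an asymptomatic, non-serious change in a mandated assessment that ends dosing, so such an event could be missing from the AE tables

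*Protocol*

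**What the plan says.** Section 12.2.6 sets the reporting rule: changes for the worse in mandated safety assessments "should therefore only be reported as AEs if they fulfill any of the SAE criteria". The reason given is that results of mandated assessments are summarized in the study report anyway. The same section has three other routes to an AE:

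- When a vital-sign or laboratory change comes with symptoms or signs, "the symptom or sign will be reported as an AE and the associated vital sign or laboratory result will be considered as additional information".
- A clinically relevant deterioration in a parameter that is not mandated is reportable even without symptoms.
- A finding at physical examination is reportable ("Any new or aggravated clinically relevant abnormal medical finding at a physical examination").

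Being the reason for discontinuation is not among these routes.

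Section 7.6.3 lists the situations in which a subject may be taken off the study drug. One is "Any significant and clinically relevant changes in the safety parameters (e.g., ECG, blood pressure, pulse, laboratory assessments and AEs", where these make further dosing unjustified. After the study-specific withdrawal criteria, the last of which is Potential Hy's Law, the section ends: "The appropriate AE form in the case report form (CRF) is to be completed".

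Section 12.2.3 makes withdrawal because of an AE a yes/no field of the AE record. Section 11.10.1 lists and counts AEs leading to discontinuation.

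**The concern.** Suppose a subject has a clinically relevant change in pulse or blood pressure after dosing, without symptoms and short of any SAE criterion, and the investigator stops dosing because of it. Section 7.6.3 foresees this case and points to the AE form. Section 12.2.6, as written, tells the site not to report it as an AE. Whether the event is counted then depends on which section the site follows.

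One of the two secondary objectives (section 6.2) is a comparison of safety and tolerability between the OD tablet, with and without water, and the IR tablet. AEs and vital signs are the only safety measures scheduled within the treatment periods (Table 1). A change severe enough to end dosing is the kind of event that a reader would expect to find in the table of AEs leading to discontinuation. Without an AE record there is also no intensity rating and no causality rating for it. An analysis plan cannot repair this later, because the record would never have been made.

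**Working it through.** The protocol gives no figure on this point, so the check sets the rules side by side for one case: an asymptomatic, non-serious change in a mandated vital sign that leads the investigator to stop dosing.

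1. **Is it foreseen?** Yes. Section 7.6.3 names blood pressure and pulse and sets no seriousness condition. Section 7.6.4 also treats changes in safety parameters as a reason for withdrawal distinct from AEs.

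2. **Does 12.2.6 let it be an AE?**
   - SAE criterion: no, by assumption. Stopping the drug does not make it one either, since Appendix 15.1 says that stopping alone does not make an event medically important.
   - Accompanying symptom or sign: none, by assumption.
   - Non-mandated parameter: no, because vital signs are on the schedule.
   - Physical-examination finding: no.

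   So the case is not reportable under section 12.2.6.

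3. **Does 7.6.3 call for an AE form?** That depends on how far its last sentence reaches.
   - If it covers every listed situation, the two sections conflict directly.
   - If it covers only the study-specific criteria just above it, the vital-sign case needs no AE form. The sections then agree, but the event goes unrecorded as an AE. Some conflict is still left over Potential Hy's Law, which is defined by laboratory values alone. Appendix 15.3 reports it as an SAE in some outcomes, but where an agreed alternative explanation is not itself an AE, it asks only for a note of that explanation on the CRF.

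   On either reading, section 12.2.6 has no route for the case in step 2.

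4. **What happens in the tables?** The withdrawal flag (12.2.3) and the summary of AEs leading to discontinuation (11.10.1) both draw on AE records. No record means no entry in either.

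5. **Where does the event remain visible?**
   - Section 11.6: withdrawals are summarized with reasons and discontinuations are listed with exit date and reason. No split by treatment is stated.
   - Section 11.10.2: vital signs are listed with flags and summarized by treatment and time-point. Descriptive statistics do not identify the subject whose dosing was stopped.
   - Section 12.1.3: an expert review for other significant AEs covers vital signs and laboratory data, but it is a matter of judgment and comes after the fact.

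6. **Which assessments matter in practice?** ECG and laboratory tests are scheduled only at screening and at follow-up or early termination (Table 1). Among scheduled tests, mainly vital signs can trigger a mid-study stop. An ECG or laboratory trigger would come from an unscheduled test, and section 12.2.6 does not make clear whether that counts as mandated.

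7. **Scale.** One event among 42 planned subjects: 1/42 = 0.0238, or 2.4%.

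**The case against.** The best defence is that the rule in section 12.2.6 is a deliberate and common choice: mandated results are reported elsewhere, so they need not be duplicated as AEs. The list in section 7.6.3 also includes the subject's own decision and severe noncompliance, where no AE need exist, so the AE-form sentence can fairly be read as applying where relevant. The data are not lost either, as disposition, vital-sign outputs and the expert review all remain. Much of this stands. It limits the point to the AE tables, and it means that a flat statement that a site cannot obey both sections would be too strong. It does not supply the missing exception.

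A reader might infer more from the text, and the documents do not support it:

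- **That section 12.1.1 contradicts section 12.2.6.** Section 12.1.1 counts "the abnormal results of an investigation (e.g., laboratory findings, ECG" among undesirable medical conditions, but it defines what an AE can be. Section 12.2.6 governs when a mandated result is reported as one.
- **That section 12.2.6 contradicts itself.** The physical-examination sentence reads as a specific exception after a general rule.
- **That the summary premise fails for ECG.** Section 11.10.2 does say "12-Lead ECG results will be listed for each subject", but the general rule in section 11.2 provides frequency counts for each qualitative variable, and the normal/abnormal evaluation is one.
- **That ECG signals bearing on the treatment comparison are hidden.** Scheduled ECGs fall only at screening and at follow-up or early termination, so they could not compare the three treatments whatever the AE rule.

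**Conclusion.** The gap is real and narrow. Section 12.2.6 lacks an exception for a deterioration that ends dosing or participation, and it does not fit with section 7.6.3, which foresees such discontinuations without requiring seriousness and refers to the AE form. An asymptomatic, non-serious case, in practice mainly a vital-sign change, could be missing from the AE tables and from the count of AEs leading to discontinuation, while remaining visible in the disposition reasons and vital-sign data.

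The conclusion assumes that sites apply section 12.2.6 as written. The number of affected subjects cannot be derived from the documents; the 2.4% is the weight of a single event if all 42 subjects are dosed. Counting scheduled vital-sign readings would not measure the problem, because readings are not events. The primary bioequivalence analysis is untouched. The correction is still worth making, because an AE that was not recorded cannot be recovered at analysis.

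**What to change.** Add one clause to section 12.2.6: *a deterioration in a protocol-mandated assessment is also recorded as an AE when it is the reason for discontinuing the IMP or for withdrawal from the study.* In section 7.6.3, state which of the listed situations the AE-form sentence covers. Align both with Appendix 15.3, so that a withdrawal for Potential Hy's Law with an agreed non-AE explanation has one recording rule.

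This changes recording only. It alters no withdrawal criterion and adds no procedure. The cost is protocol wording and at most a few more non-serious AE records. Making every clinically relevant change an AE would go further than the gap requires and would replace a deliberate reporting choice. An additional ECG table is a preference and is not needed to close the gap.

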12.3. Reporting of serious adverse events

All SAEs have to be reported, whether or not considered causally related to the IMP, or to the study procedure(s). All SAEs will be recorded in the ClinBase.

If any SAE occurs in the course of the study, then investigators or other clinical unit personnel will inform appropriate AstraZeneca representatives immediately, or **no later than 24 hours** of when he or she becomes aware of it.

The designated AstraZeneca representative will work with the investigator to ensure that all the necessary information is provided to the AstraZeneca Patient Safety Data Entry Site within 1 calendar day of initial receipt for fatal and life-threatening events and within 5 calendar days of initial receipt for all other SAEs.

For fatal or life-threatening AEs where important or relevant information is missing, active follow-up will be undertaken immediately.

Investigators or other clinical unit personnel will inform AstraZeneca representatives of any follow-up information on a previously reported SAE immediately, or **no later than 24 hours** of when he or she becomes aware of it.

In addition to recording of SAEs in ClinBase, the AstraZeneca Serious Adverse Event Report – Clinical Study form for reporting an SAE to the Data Entry Site (DES) will also be used.

All information provided for the SAE sent into the DES will be in English.

The following CRF modules will be completed for each SAE report:

- Demography
- Dosing
- AE (including start and stop date/time for the AE, the investigator's causality assessment to study drug, action taken with study drug, severity and outcome)

- SAE (including serious criteria, causality assessment to study procedure any investigations, the symptoms and course of the event and any treatments given)
- Medical History
- Concomitant Medications
- LIVERRF (risk factors), LIVERSS (signs and symptoms) and LIVERDI (additional diagnostic with results) for all SAEs with a reported term of 'Potential Hy's Law' or 'Hy's Law' will be provided in a narrative form by the PI
- Any additional supporting information e.g., laboratory test results, vital signs, ECG assessments

The 'AstraZeneca first aware date' for all SAEs reported is the date that any member of the Provider or AstraZeneca first become aware of the SAE and for regulatory reporting purposes this is the 'clock start date'.

Each SAE (as Portable Document Format [PDF]) should be sent to the DES Tata Consultancy Services (TCS) preferably via secure e-mail using the mailbox e-mail address:

The e-mail should contain the following information in the e-mail header:

Subject Title: New SAE; <study code>, <SAE text>, <Country>, <Center No>, <Enrolment code>, <Randomization code>

The message in the e-mail itself should contain the following:

A NEW serious adverse event has been reported for the following subject:

Study Code:

Country: <country>

Center No: <study site number>
Enrolment Code: <SUBJECT>

Randomization Code: <SUBJECT>

SAE Description:

Seriousness Criteria:

Study Drug Causality/Additional Med Causality/other Med Causality/Study Procedure

Causality

Date SAE met criteria for serious:

AZ (= PAREXEL investigator) first aware date:

